**SIGNIFICANCE:** Most of our knowledge on BAT comes from animal studies. In small animals we know that BAT prevents obesity and improves and reverses insulin insensitivity. In humans the role of this tissue is less clear. This is because human BAT studies have been limited mainly to retrospective studies on cancer patients due to lack of safe and reliable detection techniques to study the small quantities of diffusely distributed BAT depots present in humans *in vivo*. Fusion FDG-PET/CT remains the gold-standard imaging modality for non-invasive studies of metabolically active BAT. However, this technique is intrinsically insensitive to BAT metabolism as only small amounts (less than 10%) of glucose are taken up by activated BAT. The rest of the substrate (more than 90%) is made by fatty acids released from intracellular lipid storages. As such, the activity of this tissue is clearly underestimated by FDG-PET scans. This is especially true for overweight and obese subjects, the target population for BAT, in whom the intracellular lipid storage is more abundant (brown fat cells are swollen with fat) than in lean subjects. Therefore, this tissue relies even less on circulating glucose for thermogenesis, further limiting its detectability by FDG-PET scans. More importantly, the elevated risk of ionizing radiation and radionuclide tracer radiation exposure from these scans precludes repetitive BAT screening in healthy and young subjects, scans which are needed to correctly estimate the true prevalence of BAT, to determine the physiological relevance of BAT in humans, and to test the efficacy of new anti-obesity treatments. With this proposal we aim to fulfill this need. HP xenon MRI is extremely sensitive to the more lipid rich and less thermogenically active BAT of obese phenotypes (see comparison with FDG-PET in Fig 1) and, by being non invasive, can be repeatedly used on healthy subjects to track BAT function over time. In addition it allows direct measurement of BAT cell temperature (Fig. 2) and therefore represents the only direct way we have to monitor BAT thermogenic activity.

[figure not shown]

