**INNOVATION:** MRI with hyperpolarized xenon-129 is a technique that is been used extensively in humans to detect lung ventilation function. Here we propose for the first time to use hyperpolarized xenon gas MRI to detect BAT. Xenon is an ideal BAT probe for several reasons: A) the solubility of xenon in fatty tissue is 10 times higher than in lean tissues or blood. This means that circulating xenon naturally diffuses into BAT, enabling adequate SNR for imaging. B) Xenon is an ideal blood perfusion tracer, and therefore ideally suited to detect the increase in blood flow to BAT that occurs during stimulation of BAT thermogenesis. C)

Because xenon is not intrinsic to biological tissue, HP  $^{129}\text{Xe}$  can produce background free maps of human BAT. D) The temperature sensitivity of lipid-dissolved xenon will enable us to directly measure BAT temperature and monitor thermogenic activity in real time.

*This research is innovative as it uses an entirely different approach to investigate BAT. To our knowledge we are the very first group to use hyperpolarized xenon gas to detect BAT mass and to have demonstrated HP xenon MR thermometry of fatty tissues.*

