**APPROACH: Aim1: Demonstrate BAT mass detection in human subjects.**

Our extensive preliminary studies in rodents have shown that, upon stimulation of BAT thermogenesis, an enhancement of more than 10-fold of the MR signal from xenon dissolved in BAT is observed. This enhancement is such that a background free map of this tissue can be obtained in just few seconds (Fig. 1). In addition, when compared to FDG-PET images of BAT, hyperpolarized xenon gas images were able to clearly show BAT in both lean and obese mice and, in the latter, with superior sensitivity (Fig.1b-d).

[figure not shown]
**Fig. 1** Detection of interscapular BAT by hyperpolarized xenon gas MRI (a-b) and FDG-PET (c-d) in a lean (a-c) and obese (b-d) animal. Hyperpolarized xenon gas is clearly more sensitive to the lipid-rich BAT of obese animals (b) than FDG-PET. In d) glucose uptake by BAT is substantially reduced, making it difficult to differentiate BAT from the surrounding tissue.

The broad aim of this proposal is to validate this completely new approach to detect BAT in humans. To this end we will perform HP  $^{129}\text{Xe}$ -MRI of BAT on a 3T clinical magnet using a dual tuned xenon/1H surface coil recently purchased for human BAT studies. The coil will be accurately located above the suprACLAVICULAR area to increase sensitivity to the xenon signal dissolved in the tissue beneath. Conventional  $^1\text{H}$  MRI, which will provide anatomical reference images, will be followed by HP  $^{129}\text{Xe}$  spectroscopy and imaging scans, similar to those used in our rodent studies. Before the acquisition of the xenon images, the subject will be asked to inhale a 1L bag of 100% hyperpolarized and enriched xenon from a Tedlar bag and to hold his breath for about 15-20s. During this time hyperpolarized xenon gas will diffuse from the lung airspaces to BAT in a perfusion-based manner. At the end of the 10 s from the beginning of gas inhalation we will trigger the acquisition of the MR image, which will last for about 10s. The

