same protocol will be followed during stimulation of BAT thermogenesis, which will be achieved by an MR compatible water cooling-blanket ( $\sim 15^{\circ}\text{C}$  circulating water temperature), which will be positioned on the lower abdomen/upper leg part of the subjects. The ability to detect BAT by hyperpolarized xenon gas relies on the enhancement in blood flow to this tissue that occurs during stimulation of thermogenic activity. The magnitude of this enhancement seems to be the same, irrespective of the species and of the modality of stimulation of BAT thermogenesis (NE injection of mild cold exposure). Therefore we expect to detect a similar enhancement in the MR signal from xenon dissolved in human BAT. In addition, the use of enriched xenon versus naturally abundant xenon will compensate for the possible loss in xenon polarization during blood transit time. Pre and post stimulation scans will be compared with Matlab to detect differences of more than 5% in the intensity of the dissolved phase xenon images. Detectable BAT volume will be calculated as the sum of pixels whose intensity rose by more than 5% during cold stimulation multiplied by the pixel volume ( $1 \text{ mm}^3$ ). Data will be analyzed using JMP Pro-9.0.0 software (SAS Institute). All P values presented will be two-tailed, and values less than 0.05 will be considered to indicate statistical significance. According to previous studies done in human brain and considering the increase in blood perfusion that occurs in BAT during cold stimulation as well as the higher solubility of xenon in fatty tissues, we expect to be able to obtain images with a resolution of  $0.3 \times 0.3 \text{ cm}$ , high enough to differentiate BAT from the surrounding tissues.

**Aim 2:** Demonstrate detection of BAT thermogenesis in humans.

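### Counting every pixel that rises more than 5% as a whole pixel of BAT overstates BAT volume even without noise, and most for small depots; by how much depends on voxel size, blur and depot geometry that the plan does not give

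*Combined protocol and SAP*

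**What the plan says.** The volume measure is defined under APPROACH, Aim 1: "Detectable BAT volume will be calculated as the sum of pixels whose intensity rose by more than 5% during cold stimulation". The count becomes a volume through a fixed figure for each pixel, put at 1 mm³. No reason is given for 5%, and nothing adjusts for pixels that are only partly BAT.

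The expected effect is in the same section. In rodents "an enhancement of more than 10-fold of the MR signal from xenon dissolved in BAT is observed", and for humans: "Therefore we expect to detect a similar enhancement in the MR signal from xenon dissolved in human BAT". On image detail, the in-plane figure is 0.3 x 0.3 cm, introduced by the words "we expect to be able to obtain images with a resolution of"; slice thickness is not stated.

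Three further statements bear on the point. SIGNIFICANCE speaks of "the small quantities of diffusely distributed BAT depots present in humans". INNOVATION says that "the solubility of xenon in fatty tissue is 10 times higher than in lean tissues or blood", and that hyperpolarized xenon "can produce background free maps of human BAT".

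**The concern.** The cut-off is tiny beside the expected effect. A 10-fold signal is a 900% rise, so a pixel with only a sliver of BAT passes 5% comfortably and is then booked at full volume. The edge of every depot, and any blur around it, is counted as BAT. Small and diffuse depots have the most edge relative to their interior, and those are the depots the plan describes.

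At stake is the plan's only defined measure of BAT mass, the quantity named in Aim 1. A bias that varies with depot size does not cancel between subjects. It would also distort changes in BAT mass under treatment, one of the later uses named at the end of the APPROACH section.

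**Working it through.** The documents state no BAT volume or bias figure, so there is nothing to reproduce first.

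**Inputs from the documents:** cut-off 5%; fold-rise E = 10; in-plane resolution 3 mm; multiplier 1 mm³ (all APPROACH, Aim 1).

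**Assumed, because not given:** spherical depot of 10 or 20 mm diameter; slice thickness; image blur (3 mm full width at half maximum where used); ratio r of baseline BAT signal to that of neighbouring tissue (r = 1, range 0.1 to 10). The solubility statement points to r above 1 against lean tissue or blood.

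**Step 1: smallest BAT share that passes.** For a pixel with BAT fraction f and stable surroundings,

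rise = f·r·(E − 1) / (f·r + 1 − f), set equal to 0.05.

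- r = 1: f = 0.05/9 = 0.56%.
- r = 10: 90f = 0.05(1 + 9f), so f = 0.05/89.55 = 0.06%.
- No background signal: any f above 0.
- r = 0.5: 1.1%; r = 0.1: 5.3%. The share is under 1% once r is about 0.55 or more.
- r = 1 with surrounding signal falling 20% in the cold: 2.7%.
- E = 2, r = 1: 0.05/1 = 5%.

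**Step 2: closed-form ceiling without blur.** If every touched pixel of size a × b × c counts, the expected counted volume for a sphere of radius R, divided by the true volume, is

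[abc + 2R(ab + bc + ca) + πR²(a + b + c) + (4/3)πR³] / [(4/3)πR³].

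For 3 mm cubes:
- R = 5 mm: (27 + 270 + 706.9 + 523.6)/523.6 = 2.92.
- R = 10 mm: (27 + 540 + 2827.4 + 4188.8)/4188.8 = 1.81.

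**Step 3: the 5% rule itself.** Noise-free simulation over random grid positions, r = 1, correct pixel volume; counted over true volume:

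| Pixels | Blur | E | 10 mm sphere | 20 mm sphere |
|---|---|---|---|---|
| 1 mm cubes | none | 10 | 1.4 | 1.2 |
| 3 mm cubes | none | 10 | 2.4 to 2.5 | 1.6 |
| 3 × 3 × 10 mm | none | 10 | 4.2 | 2.3 |
| 3 mm cubes | 3 mm | 10 | 5.0 | 2.5 |
| 1 mm grid | 3 mm | 10 | 4.1 | 2.3 |
| 3 mm cubes | none | 2 | 2.0 | 1.5 |
| 3 mm cubes | 3 mm | 2 | 2.9 | 1.9 |

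Long cylinders of the same diameters, without blur, give 1.8 and 1.4 at 3 mm in-plane and 1.2 and 1.1 at 1 mm.

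**Step 4: compression between subjects.** A 20 mm sphere has (20/10)³ = 8 times the volume of a 10 mm sphere. At 3 mm cubes the rule reports 8 × 1.62/2.42 = 5.4 times, or 8 × 2.55/4.98 = 4.1 times with blur.

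**Step 5: the multiplier.** A pixel with a 3 × 3 mm face has a volume of 1 mm³ only if the slice is 1/9 = 0.11 mm thick. Counting 3 mm cubes at 1 mm³ each turns the Step 2 ceilings into 2.92/27 = 0.11 and 1.81/27 = 0.07 of the true volume, an understatement.

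**Step 6: alternatives, 3 mm cubes, pure-BAT depots of 10 and 20 mm.** Weighting each pixel by its absolute rise over the depot's peak absolute rise gives 0.98 to 1.04 times the true volume. A half-maximum contour of the absolute rise gives about 0.77 to 0.98.

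**The case against.** The strongest reply is that the size of the bias is not in the documents. They give no depot diameter, shape, slice thickness or blur, and the stated pixel volume of 1 mm³, if it reflects true resolution, leaves only about 1.1 to 1.4 times. This stands, so every fold figure here is conditional. It does not remove the bias. The plan itself expects 3 mm in-plane resolution, and a 1 mm grid laid over a 3 mm blur still gives 4.1 and 2.3 times.

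A second reply is that, taken literally, the plan errs the other way, since 3 mm pixels multiplied by 1 mm³ give too small a volume. This also stands. A reader might infer that the reported volumes will be too high as written; the documents do not support that until the two figures are reconciled. Correcting the multiplier alone, however, would expose the upward bias.

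Third, a reader might infer that the whole Aim 1 result, and the planning of later trials, rests on this volume. It does not. The closing part of the APPROACH section carries forward the standard deviations of the signal increase and of the temperature increase, and it also counts positive subjects. For a 12-subject feasibility study of detection, that limits the damage.

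Fourth, a weighted sum is not automatically better. The plan defines the rise as a percentage, and percentage weights still leave 1.3 to 2.5 times when baseline BAT signal is 10 times its surroundings. With no background they change nothing, because every touched pixel shows the same percentage rise. The weights must therefore use the absolute rise.

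**Conclusion.** The concern holds in mechanism and direction. At the rise the plan expects, and with baseline BAT signal similar to or above its surroundings, the rule counts pixels containing under 1% BAT at full volume, which inflates volume without any noise.

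For an assumed 1 to 2 cm sphere and the correct pixel volume, the overstatement is about 1.6 to 2.5 times at 3 mm cubic pixels, up to about 5 times with an assumed 3 mm blur or thick slices, and about 1.1 to 1.4 times at true 1 mm resolution. None of these is a figure of the plan. What follows from the plan without choosing a depot size is that the bias is larger for smaller depots, so it compresses between-subject differences in its defined BAT volume. The signal-increase and temperature standard deviations are unaffected.

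**What to change.** Under APPROACH, Aim 1:

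1. State the actual voxel dimensions, including slice thickness, and reconcile the 1 mm³ multiplier with the 0.3 x 0.3 cm resolution.
2. Use the 5% threshold only to detect a depot.
3. Compute volume as the sum over the depot's pixels of (absolute signal rise / peak absolute rise in that depot) × actual pixel volume, corrected for coil sensitivity where possible. A half-maximum contour of the absolute rise is a simpler alternative.
4. Call the result an effective volume, and report the 5% count beside it.

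The cost is a little Matlab code and no extra scans or subjects, plus a sensitivity map if coil correction is done. The limits should be stated:

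- Without coil correction, surface-coil fall-off makes the weighted sum understate larger depots: about 0.75 times at 20 mm with an assumed 25 mm fall-off.
- If the depot is only partly BAT, its peak pixel is not pure BAT and volume stays overstated: about 1/0.4 = 2.5 times at 40% BAT, against 3.9 to 5.8 times under the 5% rule.
- Very small depots also stay overstated: 1.1 to 1.8 times at 6 mm, against 3 to 9.6 times.
- So do small depots in thick slices: about 1.3 to 1.7 times for a 10 mm sphere at 3 × 3 × 10 mm, depending on where the slices fall, against about 4.2.

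In each of these cases the weighted sum is closer to the truth than the 5% count.

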**Specific Aim 1:** Demonstrate BAT mass detection in human subjects. For this aim we will implement hyperpolarized xenon imaging on our clinical scanner and we will compare the images obtained before stimulation of BAT thermogenesis with those obtained during stimulation of BAT thermogenesis. Our working hypothesis is that, during stimulation of BAT thermogenesis the lipophilic gas will accumulate in the highly perfused BAT tissue enabling us to clearly delineate it.

**Specific Aim 2:** Demonstrate detection of BAT thermogenesis in humans. For this aim we will measure BAT temperature by measuring the chemical shift of lipid-dissolved xenon. Our working hypothesis is that, during stimulation of BAT thermogenic activity, changes in BAT temperature would be detected as a shift in the resonance frequency of lipid-dissolved xenon.

By the end of the proposed project we expect to have demonstrated the feasibility of HP xenon

MRI detection of human BAT mass and thermogenic activity. These studies will also provide preliminary data for powering a future clinical trial with which we aim to investigate the incidence and activity of this tissue in the human population.

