This feasibility study will allow us to estimate the standard deviation for the increase in signal from xenon dissolved in BAT and for the increase in BAT temperature that will then be used to power future trials to investigate the incident of this tissue in the healthy human population and the association between BMI and BAT thermogenic activity. For these aims we plan on enrolling a total of 24 healthy subjects (12 for aim 1 and 12 for aim 2) with a BMI ranging between 18 and 28. Twelve is the minimum sample size recommended in the absence of prior information on which to base our sample size calculation. With 12 subjects per group we should be able to obtain positive results (with a 95% confidence interval) on at least 9 subjects if the true prevalence of BAT is 90% (expected prevalence), and on at least 3 subjects if the true prevalence of BAT is much smaller and close to 50% (estimated by FDG-PET scans).

By the end of the study we expect to have fully assessed the potential of HP xenon to detect BAT mass and activity and to have developed an imaging protocol that can be used in studies aimed to investigate the prevalence of this tissue in humans, its connection with other metabolic diseases such as diabetes, and to study the response to treatments aimed to counteract obesity by increasing BAT mass and or function.

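### Aim 1 converts pixel counts to BAT volume at a fixed 1 mm³ per pixel, which is not reconciled with the expected 0.3 × 0.3 cm xenon image resolution, so absolute BAT volumes may be mis-scaled

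*Combined protocol and SAP*

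**What the plan says.** Under APPROACH, Aim 1, scans before and during cold stimulation are compared to find "differences of more than 5% in the intensity of the dissolved phase xenon images". The volume measure follows directly: "Detectable BAT volume will be calculated as the sum of pixels whose intensity rose by more than 5% during cold stimulation", and that count is then "multiplied by the pixel volume ( $1 \text{ mm}^3"). A few sentences later the same section gives the resolution the investigators expect to reach, reasoning from earlier human brain work, from perfusion and from xenon's solubility in fat: "0.3 \times 0.3 \text{ cm}$ , high enough to differentiate BAT from the surrounding tissues".

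Both figures concern the xenon images. The proton images serve only as anatomical reference, and nothing says that xenon data are placed on their grid. Neither APPROACH nor the later scanning procedure (Hyperpolarized xenon-129 MRI) gives a slice thickness, matrix, field of view, interpolation or resampling step.

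**The concern.** A pixel count becomes a volume only when it is multiplied by the volume of the pixels that were counted. Here the multiplier is fixed in advance at a value that does not follow from the resolution given for the same images. An analyst who follows the text literally on native pixels would report the wrong number of millilitres, and a reader of the results could not tell whether that had happened.

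This matters because Aim 1 is stated as "Demonstrate BAT mass detection in human subjects", and detectable BAT volume is the only measure of BAT amount that the plan defines for it. The study also expects "to have developed an imaging protocol that can be used in studies aimed to investigate the prevalence of this tissue in humans", so an unexplained constant could be carried into later work.

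**Working it through.** **Inputs from the protocol (APPROACH, Aim 1)**
- Multiplier: 1 mm³ per pixel, fixed.
- Expected resolution: 0.3 × 0.3 cm, so pixel side p = 3 mm.

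**Inputs assumed, because the protocol gives none**
- Slice thickness t = 1, 3, 5 or 10 mm.
- Alternative pixel sides p = 1 and 0.5 mm, to represent interpolated grids.
- A true BAT region of 27 mL (27,000 mm³), for illustration.

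**Step 1: can the 1 mm³ be reproduced?** Voxel volume = p² × t. With p = 3 this is 9t mm³. Setting 9t = 1 gives t = 1/9 = 0.11 mm, which is 27 times finer than the in-plane resolution (3 ÷ 0.111 = 27) and is stated nowhere. The plan's constant therefore cannot be obtained from its own resolution without a further, undescribed step such as resampling.

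**Step 2: size of the error.** Reported volume = count × 1 mm³, and true volume = count × p² × t. Hence true ÷ reported = p² × t. Values above 1 mean that the reported volume is too small.

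| Pixel side p | t = 1 mm | t = 3 mm | t = 5 mm | t = 10 mm | No error at t |
|---|---|---|---|---|---|
| 3 mm (expected resolution) | 9 | 27 | 45 | 90 | 0.11 mm |
| 1 mm | 1 | 3 | 5 | 10 | 1 mm |
| 0.5 mm | 0.25 | 0.75 | 1.25 | 2.5 | 4 mm |

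The last column is 1/p².

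**Step 3: what would be reported for a true 27 mL region.** Reported mL = 27 ÷ (p² × t).

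| Pixel side p | t = 1 mm | t = 3 mm | t = 5 mm | t = 10 mm |
|---|---|---|---|---|
| 3 mm | 3 | 1 | 0.6 | 0.3 |
| 1 mm | 27 | 9 | 5.4 | 2.7 |
| 0.5 mm | 108 | 36 | 21.6 | 10.8 |

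**Step 4: if geometry differs between subjects.** Take p = 3 mm, with one subject scanned at t = 3 mm and another at t = 5 mm, each with a true 27 mL region. The fixed constant reports 27/27 = 1.0 mL and 27/45 = 0.6 mL, a spurious ratio of 1.0/0.6 = 1.67. Multiplying by each scan's own voxel volume gives 27 mL for both.

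**Step 5: what the constant does not touch.** The 5% rule is applied pixel by pixel before the multiplication, so which pixels count is unaffected. With one geometry for all Aim 1 subjects, the error is a single scale factor and the ranking of subjects is preserved. The quantities intended for powering later trials are those needed to "estimate the standard deviation for the increase in signal from xenon dissolved in BAT and for the increase in BAT temperature"; volume is not among them. The choice of 12 subjects per aim does not use volume. No stated test or threshold is expressed in mL. Whether the count of positive subjects is affected cannot be checked, because the plan does not say how pixels or volume make a subject positive.

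**The case against.** The strongest reply is that resolution and reconstructed pixel size are different things. Images with a true resolution of 3 mm may be interpolated to a finer grid, and if that grid has 1 mm³ voxels the constant is exactly right. The 0.3 cm figure is also a forecast, not a scan setting, so it cannot prove the constant wrong. All of this stands: mis-scaling is possible, not demonstrated. But the reply depends on a processing step that the plan does not describe, and a literal reading on native pixels at the plan's own resolution gives the wrong volume.

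It is also fair that slice thickness, the alternative grids and the 27 mL region are assumptions, and that the resulting range, from 4-fold overstatement to 90-fold understatement, mostly shows that the voxel size is unknown. No passage says that geometry will change between subjects. That case is a contingency suggested by an imaging protocol still under development.

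Finally, a wrong constant can be corrected after data collection once the voxel size is known, and it feeds no stated decision. That limits the seriousness of the point. It does not justify keeping a constant that the plan cannot support.

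**Conclusion.** The point holds. The fixed 1 mm³ and the expected 0.3 × 0.3 cm are not reconciled in the available text, and the constant gives a wrong absolute BAT volume if native pixels at the stated resolution are counted. The understatement is then 9t-fold, with t not stated. On a different grid it could be nil or run either way.

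The consequence is limited to absolute volumes, provided that all Aim 1 subjects are imaged with the same geometry, which is an assumption. If slice or grid varies, comparisons of volume between subjects are distorted as well. The point should be fixed, but it does not threaten the design. Confidence is high that the figures are unreconciled; whether reported volumes would in fact be wrong depends on the grid used.

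**What to change.** In APPROACH, Aim 1, replace the fixed 1 mm³ with the volume of the voxel actually counted in that scan: in-plane pixel area × slice thickness, or the resampled voxel volume if the images are interpolated before counting. State the acquired in-plane resolution, the slice thickness and any resampling, including any done offline in Matlab. If the investigators already resample to a 1 mm³ grid, saying so settles the matter.

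The cost is one line in the analysis text and one constant in the Matlab code. Scanning and sample size do not change.

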Dynamic spectroscopy data have shown the possibility to track BAT temperature over time by measurement of the chemical shift of lipid-dissolved xenon. We demonstrated for the first time MR thermometry by hyperpolarized xenon gas. This method is based on the temperature dependence of the chemical shift of lipid dissolved xenon, which we measured for the first time *in vivo* to be  $-0.2 \text{ ppm}^{\circ}\text{C}$ , (Fig 2.a), i.e. 20 times larger than that of water protons currently used for MR thermometry in lean tissues. This higher sensitivity of lipid-dissolved xenon to temperature, coupled with the lower gyromagnetic ratio of xenon (which makes xenon less sensitive to possible magnetic field in homogeneities present in fatty tissues), allowed us to detect BAT thermogenic activity in mice (Fig.2.b). To this end we will acquire dynamic spectroscopy data from xenon dissolved in BAT during stimulation of BAT thermogenesis by mild cold exposure. During these scans we will track the resonance frequency of lipid-dissolved xenon to detect changes in BAT temperature during thermogenic activity. Although in humans we expect temperature changes less than  $2^{\circ}\text{C}$ , the high sensitivity of xenon to temperature and the narrow line width can allow us to detect changes as small as  $0.2^{\circ}\text{C}$ .

**Fig.2** a) Linear temperature shift of the lipi-dissolved xenon frequency as acquired *in vivo* in an obese mouse. b. Thermogenic activity as detected by hyperpolarized xenon gas. The graph shows the resonance frequency shift of lipid-dissolved xenon and the corresponding shift in BAT temperature right after injection of NE.

For these studies the subject will inhale 4 doses of 1L each of xenon during mild cold exposure, achieved with a water cooling blanket. After inhalation, the subject will be asked to hold his breath for 15-20 seconds, during which we will trigger the acquisition of xenon spectra. The spectra will then be fitted with homemade Matlab routines to extract lipid-dissolved xenon resonance frequency that will be used to detect any change in BAT temperature.

The change in BAT temperature will then be analyzed as function of BMI to establish whether or not there is an association between BMI and BAT temperature increase (Pearson correlation and Spearman correlation coefficient calculation).

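### Aim 2 places all four spectra during cooling and does not time the first, so the plan assures only a within-cooling change, not the BAT temperature increase it intends to analyse

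*Combined protocol and SAP*

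**What the plan says.** The Aim 2 part of APPROACH describes the acquisition twice, each time under cooling: "we will acquire dynamic spectroscopy data from xenon dissolved in BAT during stimulation of BAT thermogenesis by mild cold exposure", and then "For these studies the subject will inhale 4 doses of 1L each of xenon during mild cold exposure". The fitted resonance frequency is converted to a change in BAT temperature, which is analysed to establish "whether or not there is an association between BMI and BAT temperature increase". The same section expects human changes below 2 °C and says that the method "can allow us to detect changes as small as" 0.2 °C.

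The sample-size paragraph that closes APPROACH gives the result a second use: the study is to estimate the SD "for the increase in BAT temperature that will then be used to power future trials". It assigns 12 subjects to each aim, 24 in all.

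Aim 1 is laid out differently. It plans xenon "spectroscopy and imaging scans, similar to those used in our rodent studies", and then says that the "same protocol will be followed during stimulation of BAT thermogenesis". That is a before-and-during comparison.

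**The concern.** An increase needs a reference point, and Aim 2 does not define one. The change between the first and a later cooling spectrum equals the increase reached by that later spectrum only if the first was taken before BAT began to warm. The plan neither requires nor excludes this.

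If warming has already begun, the early part of the rise is lost from every subject's value and the mean is too low. The SD carried forward then belongs to an undefined quantity. A flat series becomes ambiguous, because a subject with no thermogenesis and a subject who warmed early and reached a plateau look the same. A baseline that was not acquired cannot be recovered after scanning.

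**Working it through.** **Could another section supply the baseline?**

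- Aim 1 has scans before cooling, but in its own 12 subjects (sample-size paragraph of APPROACH; F. Number Justification).
- The practice inhalation takes place before the subject enters the scanner, with xenon of natural isotopic abundance, so it yields no spectrum.
- The section on hyperpolarized xenon-129 MRI (at least 15 min between doses) and the xenon gas budget item (spectroscopy doses every 20 min) give spacing only.
- The Aim 2 text gives a slope of -0.2 ppm per °C but no absolute frequency reference. On the text alone, a cooled spectrum does not reveal the pre-cooling temperature. The calibration figure was not available for this review, so I put little weight on this.

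**The plan's own figures.** The 0.2 °C limit corresponds to 0.2 × 0.2 = 0.04 ppm. The plan has no calculation for the temperature increase. Its one sample-size statement reproduces, with P(at least 9 of 12) = 0.974 at 90% prevalence and P(at least 3 of 12) = 0.981 at 50%, but it does not bear on this point.

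**Illustration.** From the documents: four spectra have three intervals, so the span s is 3 × 15 = 45 min or 3 × 20 = 60 min. Assumed, and not in the documents: warming follows T(t) = 1 - exp(-t/τ) after its onset, with τ from 10 to 40 min. Let d be the delay of spectrum 1 after cooling onset, L the physiological lag before BAT warms, and u = d - L.

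Reading as written: T(u + s) - T(u). Reading against a pre-warming baseline, same last spectrum: T(u + s). Early rise missed: T(u).

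Examples for a true 1 °C rise:
- u = 10, τ = 10, s = 45: exp(-1) - exp(-5.5) = 0.368 - 0.004 = 0.364.
- u = 20, τ = 40, s = 60: exp(-0.5) - exp(-2) = 0.607 - 0.135 = 0.471.

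| u (min) | Early rise missed | Reads as written (°C) | Reads against baseline (°C) | Smallest true rise reading 0.2 °C as written |
|---|---|---|---|---|
| 0 | 0% | 0.68-1.00 | 0.68-1.00 | 0.20-0.30 |
| 10 | 22-63% | 0.36-0.62 | 0.75-1.00 | 0.32-0.55 |
| 20 | 39-86% | 0.13-0.47 | 0.80-1.00 | 0.42-1.49 |

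The shortfall at u = 0 is warming still incomplete at the last spectrum; it is not caused by the missing baseline. The last column is 0.2 divided by the reading, for example 0.2/0.134 = 1.49. With d = 10 and L = 10, u = 0 and nothing is missed.

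**SD and correlation.** Further assumptions: between-subject CV of the rise 20-50%, true correlation with BMI -0.50, τ uniform on 10-40 min and unrelated to BMI (2 million simulated subjects).

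- u fixed at 10 min: the SD is 0.59-0.68 of the baseline-referenced SD; r is -0.43 to -0.49, against -0.46 to -0.50 with a baseline.
- u fixed at 20 min: SD ratio 0.41-0.63; r from -0.30 to about -0.44.
- u varying from 0 to 20 min between subjects: SD ratio 0.72-1.06; r about -0.3 to -0.4.

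For scale, with 12 subjects the 95% interval around r = 0 is ± tanh(1.96/√9) = ±0.57. The 95% interval for an SD already runs from about 0.71 to 1.70 times the estimate.

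**The case against.** The strongest reply is that following temperature during stimulation is a coherent feasibility aim, and that the plan leans towards an early first spectrum. It speaks of tracking temperature over time, and its mouse example follows the shift immediately after the stimulus. If spectrum 1 falls at or before warming onset, nothing is lost. That stands, and it is why the point is only that the plan does not assure a baseline. It remains an inference, because no section fixes the time.

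The size rests wholly on assumed inputs. That also stands: at a 10 min delay, changing only the lag from 0 to 10 min takes the missed share from as much as 63% to nothing.

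The baseline has its own weakness. Aim 1 says that detection relies on the increased blood flow under stimulation, so a pre-cooling peak may be weak or weighted to other fat. A difference from it could then mix a change of tissue with a change of temperature. The model above does not cover this.

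A reader might also infer that a future trial sized on this SD would be too small by a calculable factor. The documents do not support that. The future questions they name are the incidence of BAT and the association of BMI with its activity. Power for a correlation depends on r, not on an SD in degrees, and the SD would suit a later study with identical timing. Nor is the SD always too low: it can be slightly high when timing varies between subjects.

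**Conclusion.** The point holds in limited form. As written, Aim 2 assures a within-cooling change and names it an increase. If warming precedes spectrum 1, the mean is understated and a flat series cannot be interpreted. The SD is then mis-stated: lower if timing is fixed, lower or slightly higher if it varies. The BMI correlation is affected little at short delays, and with 12 subjects its own imprecision dominates.

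The illustrated readings of 0.36-0.62 °C at 10 min and 0.13-0.47 °C at 20 min, for a true 1 °C rise, depend on the assumed exponential curve, the time constants and the absence of a covering lag. A reader might infer that Aim 2 cannot detect thermogenesis at all, or that bias is likely. Neither follows, because the first spectrum may coincide with cooling onset. It should be fixed before scanning, because the change is cheap and the omission cannot be repaired afterwards.

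**What to change.** Make one of the already planned Aim 2 spectra a pre-cooling baseline, as Aim 1 does for its scans. Log the time of every spectrum from cooling onset. Define the increase as a named cooling spectrum minus that subject's baseline. Where the baseline peak cannot be fitted, report the within-cooling change separately, keep it out of the baseline-referenced SD and BMI correlation, and give the number of such subjects.

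This needs protocol wording and a time log, with no added inhalation. Four spectra over 45-60 min fit the stated session of about 2 hours. The costs are three cooling time points instead of four, the possibly weak or mixed baseline peak, and possibly a shorter cooling span. If cooling simply starts after spectrum 1 with spacing unchanged, a 10 min lag gives T(s - 10) = 0.58-0.99, against 0.68-1.00 for the plan as written with dose 1 at 10 min.

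If all four spectra stay during cooling, state the time of dose 1 from cooling onset and call the endpoint a within-cooling change.

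The number, volume and spacing of inhalations remain the sponsor's decision. The Aim 2 text gives 1 L per spectroscopy dose and the xenon gas budget item gives 0.5 L; these must be reconciled.
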